9.2 Missing or Inconclusive Data Handling

[Redacted content]

9.3 Definition of Baseline

Baseline measures are defined as the last measure prior to the initiation of study treatment, usually at Visit 1 screening.

9.4 Data Analysis Conventions

All data analysis will be performed by Statistics & Data Corporation (SDC) after the study is completed and the database has been locked and released for unmasking. Statistical programming and analyses will be performed using SAS® Version 9.4 or higher. Output will be provided in RTF (Rich Text Format) for tables and PDF (Portable Document Format) for tables, listings, and figures using landscape orientation. All study data will be listed by subject, treatment, and visit (as applicable) based on all enrolled subjects unless otherwise specified.

All summaries will be presented by treatment group. Summaries will be provided for demographics, medical history, concomitant medications, and subject disposition. For the purpose of summarization, medical history, concomitant medications, and AEs will be coded to Medical Dictionary for Regulatory Activities (MedDRA) 20.1 and World Health Organization (WHO) Drug Global Dictionary (Enhanced B3, September 2017), as appropriate.

Summaries for continuous and ordinal variables will include the number of observations (n), arithmetic mean, standard deviation (SD), median, minimum, and maximum. Minima and maxima will be reported with the same precision as the raw values; means and medians will be presented to one additional decimal place than reported in the raw values. Standard deviations will be presented to two additional decimal places than reported in the raw values. Summaries for discrete variables will include frequency counts and percentages. All percentages will be rounded to one decimal place (i.e., XX.X%).

All statistical tests will be two-sided with a significance level of 0.05 ($\alpha = 0.05$) unless otherwise specified. Confidence intervals (CI) for differences between treatment groups will be two-sided at 95% confidence levels where appropriate. All p-values will be rounded to four decimal places; p-values less than 0.0001 will be presented as "<0.0001"; p-values greater than 0.9999 will be presented as ">0.9999".

9.5 Adjustments for Multiplicity

Adjustments for multiple testing will not be implemented for this early phase study.

10. Disposition of Subjects

Subject disposition will be presented in terms of the numbers and percentages of subjects who were randomized, completed the study, and discontinued from the study. Subjects who are not discontinued from the study will be considered study completers. Disposition will be summarized by treatment group and for all subjects.

The number of randomized subjects in each of the analysis populations (ITT, PP and Safety) will be displayed by treatment. The ITT population uses treatment as randomized; PP and Safety populations use treatment as treated. Percentages are based on the total number of subjects randomized in each treatment group.

The number and percentage of subjects prematurely discontinued from the study and the reasons for study discontinuation will be summarized by treatment group for all randomized subjects. The reasons for study discontinuation that will be summarized include: AE, protocol violations, administrative reasons (e.g., inability to continue, lost to follow up), sponsor termination of study, subject choice, and other. In addition, any subject may be discontinued for any sound medical reason at the discretion of the Investigator (after consultation with the Sponsor) or Sponsor. A subject listing will be provided that includes the date of and reason for premature study discontinuation.

The number and percentage of subjects with any, major, and minor protocol deviations will be summarized by treatment group for all randomized subjects. The number and percentage of subjects with any protocol deviation will also be summarized for the following categories: Informed Consent, Inclusion / Exclusion and Randomization, Test Article / Study Drug Instillation and Assignment at Site, Improper Protocol Procedures at Site, Site's Failure to Report SAE / AE, Visit Out of Window, Subject's Non-compliance with Test Article, Subject's Use of Prohibited Concomitant Medication, Subject's Failure to Follow Instructions, and Other. A subject listing will be provided that includes the date and description of each deviation.

In addition, subject listings will be provided that include randomization and treatment; whether inclusion and exclusion criteria were met; and inclusion in the ITT, Safety, and PP populations.

11. Demographic and Pretreatment Variables

11.1 Demographic Variables

The demographic variables collected in this study include age, sex, race, ethnicity and iris color. Demographic variables will be summarized, overall and by treatment group, for the ITT and Safety populations, separately.

Age (years) will be summarized using continuous descriptive statistics. Age will also be categorized as follows: <65 years and ≥65 years. Age will be reported in years and calculated using the following formula:

$$\text{Age} = (\text{informed consent date} - \text{date of birth}) / 365.25 \text{ truncated as an integer}$$

The number and percentage of subjects will be presented for age category, sex, race, ethnicity and iris color. Iris color will be summarized for the right eye (OD) and left eye (OS) separately.

A subject listing that includes all demographic variables for all randomized subjects will be provided.

11.2 Baseline Variables

Baseline disease characteristics will be summarized by treatment group for the study eye (where applicable) using continuous descriptive statistics for basal Schirmer's test, Schirmer's test with cotton swab stimulation, EDS, ocular discomfort score, total OSDI® score, corneal fluorescein staining, BCVA and pupil diameter. The scales for OSDI, corneal fluorescein staining and Schirmer's test with cotton swab stimulation are described below. The scales for the efficacy endpoints of Schirmer's test, EDS, and ocular discomfort score are provided in the respective subsections in Section 14 of this SAP. The scales for the safety endpoints of BCVA and pupil diameter are provided in the respective subsections in Section 15 of this SAP.

11.2.1 OCULAR SURFACE DISEASE INDEX[®]

The OSDI[®] is assessed on a scale of 0 to 100, with higher scores representing greater disability. The OSDI[®] asks the following 12 questions at the subject level:

Have you experienced any of the following during the last week:

- 1) Eyes that are sensitive to light?
- 2) Eyes that feel gritty?
- 3) Painful or sore eyes?
- 4) Blurred vision?
- 5) Poor vision?

Have problems with your eyes limited you in performing any of the following during the last week:

- 6) Reading?
- 7) Driving at night?
- 8) Working with a computer or bank machine (ATM)?
- 9) Watching TV?

Have your eyes felt uncomfortable in any of the following situations during the last week:

- 10) Windy conditions?
- 11) Places or areas with low humidity (very dry)?
- 12) Areas that are air conditioned?

OSDI[®] will be collected for both eyes pre- treatment at Visit 1. The 5-unit scale for responses to the OSDI[®] is given by the following: 0=None of the time, 1=Some of the time, 2=Half of the time, 3=Most of the time and 4=All of the time. The total OSDI[®] score is calculated by the following:

[figure not shown]
$$\text{OSDI}^{\circledR} = \frac{(\text{sum of scores}) \times 25}{\# \text{ of questions answered}}$$

Note that the number of questions answered in the denominator should exclude those questions with a response of "N/A".

11.2.2 CORNEAL FLUORESCEN STAINING

Corneal fluorescein staining will be performed on both eyes and graded using the National Eye Institute (NEI)/Industry Workshop Scale. The scale will grade the cornea by five regions: inferior, superior, central, temporal, and nasal. The scale ranges from 0 to 3. Grade 0 indicates no staining is present. The maximum total score is 15.

Fluorescein staining scores will be summarized by region (5 regions, plus total score) for the study eye using quantitative summary statistics.

11.2.3 SCHIRMER'S TEST WITH COTTON SWAB STIMULATION

Schirmer's test with cotton swab stimulation will be performed on both eyes. Schirmer's scores are between 0 mm and 35 mm, inclusive. The result will be summarized for the study eye using quantitative summary statistics.

12. Medical History and Concomitant Medications

12.1 Medical History

Medical history will be coded using MedDRA Version 20.1.

Ocular medical history will be summarized using discrete summary statistics and presented by treatment group at the subject and event level by System Organ Class (SOC) and Preferred Term (PT) using the ITT population. Non-ocular medical history will be similarly summarized at the subject and event level. If a subject reports the same PT multiple times within the same SOC, that PT will only be reported once within that SOC. As with the PT, if a subject reports multiple conditions within the same SOC, that SOC will only be reported once.

[figure not shown]
Listings of medical history will be generated separately for ocular and non-ocular data.

12.2 Prior and Concomitant Medications

Concomitant medications are defined as those medications listed as having been taken 1) prior to initiation of study drug administration and continuing for any period of time following the first administration of study drug or 2) at any time following the first administration of study drug.

Concomitant medications will be coded using WHO Drug Global B3 Dictionary September 2017 and summarized to the therapeutic drug class (Anatomical Therapeutic Chemical [ATC] 4 classification) and preferred name. If the ATC 4 classification is not provided, the next lowest classification that is provided in the coding dictionary will be used. The preferred name will be defined as the active ingredient; if the active ingredient is not provided or includes more than two ingredients (eg, multivitamins) then the drug name will be summarized as the preferred name. Any uncoded terms will be summarized under the ATC classification and preferred name of "Uncoded."

Concomitant medications will be summarized using the ITT population. Prior medications will be provided in subject listings, but will not be summarized. Ocular and non-ocular medications will be summarized separately. Medications will be tabulated for each treatment group using frequencies and percentages. Subjects may have more than 1 medication per ATC text. At each level of subject summarization, a subject will be counted once if he/she reports 1 or more medications. Percentages will be based on the number of subjects in each treatment group. Listings of concomitant medications will be generated separately for ocular and non-ocular data.

13. Treatment Exposure

13.1 Treatment Exposure

Percent exposure (%) will be assessed by calculating the volume of dose administered and comparing that to the volume expected as follows:

$$\text{Percent Exposure (\%)} = \frac{\text{Volume Administered (\mu L)}}{\text{Volume Expected (\mu L)}} \times 100\%$$

The volume administered will be calculated by adding the volume administered in the left and right nostrils in μL Visits 1 and 2. The volume expected at each visit is 200 μL (100 μL in each nostril) and hence the volume expected is 400 μL for subjects that complete the study and 200 μL for subjects that discontinue prior to Visit 2.

Volume of study drug administered and volume expected for each subject exposed to study drug will be summarized with continuous descriptive statistics for each treatment group, using the Safety population. The number and percentage of subjects with percent exposure $\leq 80\%$ and $> 80\%$ will also be summarized by treatment group. A subject listing of percent exposure, volume administered, and volume expected will also be produced.

14. Efficacy Analyses

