7.1.2 Dispensation Schedule

- At Visit 1, qualified subjects will be randomized and the first dose of study drug will be administered in office.
- At Visit 2, subjects will receive their second dose of study drug during CAE® exposure.

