 - Treatment with Investigational drug/placebo will be administered upon participant reporting an Ocular Discomfort score ≥ 3 at two or more consecutive time points in at least one eye during CAE® exposure (if a participant has an Ocular Discomfort rating of 3 at time = 0 for an eye, s/he must report an Ocular Discomfort rating of 4 for two consecutive measurements for that eye) using the ██████████ Scale. Participant will resume symptom assessments 1 minute after the application ends every 5 minutes.
- BCVA
- Slit lamp biomicroscopy

- Intranasal Examination
- Urine Pregnancy Test (if applicable)
- Concomitant Medications
- AE Query
- Study exit

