8.6 Subject Disposition

8.6.1 Completed Subjects

A completed subject is one who has not be discontinued from the study.

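### SAP 13.1 expects 400 µL from every completer, so a subject who attends Visit 2 but never meets the dosing trigger is scored 50% exposed, while one who leaves before Visit 2 after the same 200 µL is scored 100%

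*SAP*

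**What the plan says.** SAP 13.1 defines percent exposure as volume administered over volume expected, times 100. Administered volume is summed over both nostrils and both visits. There are only two expected volumes. The per-visit amount is 200 µL (100 µL "in each nostril) and hence the volume expected is 400" µL for a subject who completes the study), and it is 200 µL in total "for subjects that discontinue prior to Visit 2". Both volumes are summarised as continuous variables in the Safety population. "The number and percentage of subjects with percent exposure" at or below 80%, and above 80%, are also tabulated by arm. The table shell is Table 14.3.6.

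Completion does not depend on receiving the second dose. SAP Section 10 states: "Subjects who are not discontinued from the study will be considered study completers". Protocol 8.6.1 agrees: "A completed subject is one who has not be discontinued from the study". The disposition summary in SAP Section 10 covers "subjects who were randomized, completed the study, and discontinued from the study", with no row for subjects who attended Visit 2 and were not dosed.

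On the Visit 2 dose itself the documents differ. Protocol 7.1.2 states it without condition: "At Visit 2, subjects will receive their second dose of study drug during CAE". Protocol 5.1 is likewise unconditional. The visit procedures in Protocol 8.3.1 make it conditional: "Treatment with Investigational drug/placebo will be administered upon participant reporting an Ocular Discomfort score" of at least 3 at two or more consecutive time points in at least one eye, with a stricter rule for an eye that starts at 3. SAP 14.1.2 repeats the trigger and says what happens to the Eye Dryness Score (EDS) data of a participant who does not qualify.

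**The concern.** The 400 µL denominator assumes that two doses come due for every completer. Under the trigger as written in Protocol 8.3.1 and SAP 14.1.2, that is not so. A subject can attend Visit 2, sit through the CAE exposure, never reach the trigger, leave undosed as those sections direct, and still be a completer. SAP 13.1 makes no exception for this subject, who is then counted as having missed half the expected drug.

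At stake is what the exposure table means. Its ≤80% class is there to show under-dosing. As defined, it would mix real under-dosing with subjects handled exactly as the visit procedures state. Two subjects with identical administered volume would also land in opposite classes, depending only on whether they came back for Visit 2.

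**Working it through.** **Inputs from the documents.** 100 µL per nostril, two nostrils, two visits (SAP 13.1). Class boundary 80% (SAP 13.1). About 160 randomized, 40 per arm, 5% dropout, about 38 per arm completing (Protocol 10.3).

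**The plan's own figures.** Per visit: 100 × 2 = 200 µL. Two visits: 200 × 2 = 400 µL. Completers per arm: 40 × 0.95 = 38. All three reproduce, so the arithmetic is right. The question is to whom 400 µL applies.

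**Scores under SAP 13.1:**

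| Subject | Administered (µL) | Expected (µL) | Exposure | Class |
|---|---|---|---|---|
| Both doses in full | 400 | 400 | 100% | >80% |
| Full Visit 1 dose, attends Visit 2, does not qualify | 200 | 400 | 50% | ≤80% |
| One nostril only at both visits | 100 + 100 = 200 | 400 | 50% | ≤80% |
| Full Visit 1 dose, leaves before Visit 2 | 200 | 200 | 100% | >80% |

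The second and third rows cannot be told apart by the score. The second and fourth received the same volume and fall in opposite classes.

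**How many subjects.** The share q of Visit 2 attenders who do not qualify is not given, so I assume a range of 0 to 30%. I also assume that all dropouts leave before Visit 2 (2 of 40 per arm, so 4 × 38 = 152 attend) and that every dose that comes due is given in full.

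- Non-qualifiers placed in the ≤80% class: 152q.
- Mean expected volume as written: (2 × 200 + 38 × 400)/40 = 390 µL, whatever q is.
- Mean administered volume: 390 − (38/40) × 200q = 390 − 190q µL.
- Apparent mean shortfall: 190q µL.

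| q | In ≤80% class, of 160 | Mean administered (µL) | Mean expected (µL) | Apparent shortfall (µL) |
|---|---|---|---|---|
| 0% | 0 | 390 | 390 | 0 |
| 5% | 7.6, about 8 (4.75%) | 380.5 | 390 | 9.5 |
| 10% | 15.2, about 15 (9.5%) | 371 | 390 | 19 |
| 20% | 30.4, about 30 (19%) | 352 | 390 | 38 |
| 30% | 45.6, about 46 (28.5%) | 333 | 390 | 57 |

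By construction no dose that came due was missed, so every entry in the last column is an artefact of the denominator. If expected volume is 200 µL for a non-qualifier, the score is 200/200 = 100%, the non-qualifiers leave the ≤80% class, and the shortfall is 0 at every q.

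**The case against.** The strongest reply is that little depends on this number. Percent exposure feeds no visible decision: the per-protocol population (SAP 8.2) rests on deviations and completion, and compliance in Protocol 8.5 rests on used and unused drug. Administered volume is correct. Much can also be recovered from planned output. SAP 13.1 lists both volumes by subject. The instillation listing (16.2.5.1) and the CAE listings should separate a non-qualifier from a one-nostril subject. Completers in Table 14.1.1 set against n in Table 14.2.2.1 would roughly give the non-qualifiers per arm. All of this stands, and it keeps the severity low. It does not make the tabulated class correct.

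The size is also unknown. Most inclusion criteria are redacted, and any symptom threshold among them could make q small. If q is near 0, the point is trivial.

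One might say that 400 µL is simply the planned maximum. SAP 13.1 does not follow that logic: it already lowers the expectation to 200 µL for early leavers, for whom no second dose came due. Nor does it help if a site records a non-qualifier as discontinued. Nothing directs this, and such a subject did not leave before Visit 2, so SAP 13.1 would supply no expected volume at all.

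Protocol 5.1 and 7.1.2 can be read as summaries, with Protocol 8.3.1 as the operating detail. That is a fair reading, but the 400 µL rule matches the summaries and not the detail, so the texts still need to be aligned.

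A reader might go further and infer that the EDS sensitivity analysis is compromised, because SAP 14.1.2 sets non-qualifiers' EDS to missing and then imputes in the ITT population. The documents do not support that conclusion. SAP 9.2 and the imputation code are redacted, so whether non-qualifiers enter the imputation cannot be determined. The primary EDS analysis uses observed data and is unaffected. In an illustrative simulation, imputing the non-qualifiers moved the mean estimate by at most 0.07 mm from the observed-data result, against a standard error of about 5 to 6 mm. That simulation assumed two arms of 40 with two dropouts each, residual SD 20 mm, effect −10 mm, q of 10 to 30%, and 20 regression-based imputations standing in for MCMC.

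**Conclusion.** The point holds as a low-severity error in a descriptive safety table. The stated rule gives a misleading figure for a type of subject the SAP itself foresees: 50% for a non-qualifier handled as written, against 100% for an early leaver with the same 200 µL. This follows from the text and needs only a full first dose and the documents' own definition of a completer.

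The number affected is assumption: about 0, 8, 15, 30 or 46 of 160 at q of 0, 5, 10, 20 or 30%, with 5% leaving before Visit 2. The effect is on the ≤80% and >80% classes, the comparison of expected with administered volume in Table 14.3.6, and the subject listing. It should not be read as a threat to either primary endpoint, to the per-protocol population, or to the EDS imputation.

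**What to change.** First, reconcile Protocol 5.1 and 7.1.2, which state the Visit 2 dose without condition, with Protocol 8.3.1 and SAP 14.1.2, which make it conditional. Which rule applies is for the sponsor to settle.

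Then define expected volume in SAP 13.1 from the doses that came due for each subject under the reconciled rule. As Protocol 8.3.1 and SAP 14.1.2 now read, that would be 200 µL for a subject who attended Visit 2 and did not qualify. Report the number and percentage not qualifying, by arm, next to the exposure table, so that low exposure and non-qualification can be told apart.

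The cost is a few sentences of SAP text, one changed denominator and one added count. The CAE discomfort scores and administered volumes are already collected, so no new data are needed.

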14.1 Primary Analysis

The two primary endpoints are:

[figure not shown]
- Schirmer's Test results at Visit 1
- Eye Dryness Score during Controlled Adverse Environment[®] (CAE[®]) at Visit 2

For both primary endpoints, treatment comparisons between active and placebo will be calculated as active – placebo. For Schirmer's Test, a positive difference indicates a better score for the active treatment. For EDS, a negative difference indicates a better score for the active treatment.

14.1.1 SCHIRMER'S TEST

Schirmer's test with topical anesthesia will be performed pre- and post-treatment at Visit 1. Schirmer's test result will be summarized by time point (pre- and post-treatment at Visit 1), and treatment with quantitative descriptive statistics (n, mean, median, standard deviation, minimum and maximum).

 model will be used to compare the change in Schirmer's Test pre- to post-treatment in the study eye between each dose of OC-02 Nasal Spray and placebo treatment groups. The  model will include baseline Schirmer's Test (captured at Screening) and study

site as covariates. Least Squares Means (LS Means) for each treatment, the corresponding 95% confidence intervals (CI), and the estimated treatment differences between each dose of OC-02 Nasal Spray and placebo will be calculated from this [REDACTED] model. In addition, the study site by treatment interaction will be explored in a separate model to evaluate how the treatment effect may differ across study sites. In the case of a significant interaction at the 0.05 level, analyses will be performed by site to understand how the treatment effect differs across sites. The differences in means, two-sided 95% CIs for the difference in means and p-values will be reported. Pairwise t-tests from the ANCOVA model will be used to compare treatment and placebo groups.

The primary analyses will be performed on the ITT population on observed data only. The SAS code for the analysis is:

[REDACTED]

[REDACTED] analysis estimates of pre- to post-treatment changes will be displayed in a bar chart with standard error bars by treatment group. Two sample t-tests and non-parametric Wilcoxon rank sum tests will be used to compare treatments as unadjusted sensitivity analyses. The number and percentage of subjects with a greater than 10 mm and greater than 20 mm increases relative to baseline will also be reported by treatment group. The percentage of subjects in each treatment group will be compared using Fisher's Exact Test. Sensitivity analyses will also be performed on the ITT population with multiple imputation (MI) to impute missing data, as well as the PP population with observed data only.

[figure not shown]

The multiple imputation sensitivity analysis will use MCMC imputation to have a full accounting of the ITT population at Visit 1. The MCMC method will be performed using the SAS procedure PROC MI. The SAS code for obtaining multiple imputation data is:

```
[REDACTED SAS CODE]
```

After obtaining twenty complete data sets and calculating changes from baseline, the following SAS code will be used to run the [REDACTED] model on each data set and combine the results from the twenty analyses:

```
[REDACTED SAS CODE]
```

[REDACTED]

Schirmer's test will also be analyzed in the fellow eye using the ITT and PP populations with observed data only.

Stratified analyses of Schirmer's test will include [REDACTED] analysis, t-tests and Wilcoxon rank sum tests using the ITT population with observed data only, in the study eye and fellow eye, separately. The following strata will be used:

[figure not shown]
- Inferior corneal staining < 1.5
- Inferior corneal staining ≥ 1.5
- Baseline EDS < 60
- Baseline EDS ≥ 60

